## Analysis plan

### Primary Analysis

We will assess the impact of Family Safeguarding Model on the primary outcomes of interest  $Y_{iat}$  in the following GLMM regression framework:

$$\text{logit}(Y_{iat}) = \beta_0 + \alpha_{0a} + \beta_1 FS_{iat} + \sum_{i=1}^5 \beta_{i+1} I(t = i) + \gamma X_{iat} + \rho Z_{at} + \varepsilon_{iat}$$

Where

- $Y_{iat}$  is a binary indicator that equals 1 if the child entered care within 24 months of their first referral in the trial period, and 0 otherwise.
- $\alpha_{0a}$  is a (normally distributed) random intercept at the level of the cluster. This random effect estimates the stochastic variation of individual clusters around the conditional mean of the clusters.
- $\beta_2 - \beta_6$  are a series of indicator variables adjusting for time trends by introducing dummy variables for each time after the baseline period  $t = 0$ .
- $FS_{iat}$  is a binary indicator that is equal to 1 if the child had its first referral during the trial period after the local authority implemented Family Safeguarding (and 0 if before).
- $X_{iat}$  is a vector of individual and household level characteristics that may also influence the outcome, such as age of the child, gender, and household SES.
- $Z_{at}$  is a vector of time-varying local authority characteristics, such as the number of children per local authority or the turnover rate of staff.
- $\varepsilon_{iat}$  are the errors at time  $t$  for individual  $i$ .

The GLMM is an extension of the GLM for analysing correlated data. The unit of analysis is at the individual level to optimise the power to detect an effect within the constraints of the project. We use a logistic regression within the GLMM framework to account for the binary nature of our outcome variable and because the baseline rate is low.

We will judge the statistical significance of the treatment effects applying a significance level of 5%. Due to the small number of clusters, we cannot cluster or bootstrap standard errors via any conventional method. However, we will consider whether or not applying a wild bootstrap with a correction for the small number of clusters is appropriate in this instance. Our sensitivity analysis will consider different evaluation approaches that are discussed in detail below.

There is a risk of non-compliance, e.g. local authorities may implement some or all aspects ahead of their agreed Operationally Live date, or fail to implement some elements. As stated above, we will adjust the date we consider Family Safeguarding has been implemented, if it

---

 Population as described above.

 We consider the referral date to be the relevant date according to which the relevant time dummy is determined.

 Children can only occur once in our evaluation, i.e. that we consider the first referral.

becomes apparent that there have been significant changes in terms of the timings of the models core activities. This will only be done with the agreement of the Department for Education and in consultation with the model developer. However, outside of this we will take an intention-to-treat approach, and will not, in our primary analysis consider other elements of non-compliance. However if the IPE shows that there have been substantial instances of non-compliance, we will consider running complier average causal effect (CACE) analysis to account for this. This would however be secondary analysis.

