### **Sample size / MDES calculations**

*NB: These power calculations were conducted with the 'steppedwedge' package in Stata. We will conduct simulations to ensure the accuracy of these and update the trial protocol before any outcome data is collected. This could lead to changes in the minimum detectable effect size (MDES).*

---

 Note that the cases do not need to be open after assessment, i.e. we expand the population of interest beyond our analytical sample for this outcome measure.

	Proportion of children who become CLA within 18 months of referral start date
MDES	0.0105
Baseline measures	0.06
Intraclass correlation (ICC) Local authority	0.00722
Alpha	0.05
Power	0.8
One-sided or two-sided?	Two-sided
Level of intervention clustering	Local authority
Number of clusters	5
Average cluster size (children per local authority across all time periods)	10,200
Average cluster cell size (children per local authority per time period)	1,700
Sample Size (children) Total	51,000

We are powered to detect an effect size of 0.0105, or a 1.05 percentage point decrease or increase in the proportion of children who become looked after within 18 months of referral start date.

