### ***Sample size and cluster size***

The sample size was derived from the estimated baseline population for our primary outcome, which is the number of children who have been referred in a six month period. We take the average across local authorities that form part of our sample to calculate the average cluster size. The sample size is derived from the average cluster size times the number of local authorities in the trial and the six periods of the stepped-wedge implementation.

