#### Vector of individual level covariates of the child or young person

- Gender (included as a binary indicators for male, female, or other/undetermined)
- Ethnicity
- Age in months
- Academic year
- Disabled status (included as a binary indicator: 0=No, 1= Yes)
- Eligibility for free school meals (included as a binary indicator: 0=No, 1=Yes, if pupil has ever been recorded as eligible for free school meals on Census day in any Spring Census up to the pupil's current year), Pupil Premium eligibility (for Reception, Year 1 and Year 2)
- Is child an Unaccompanied Asylum Seeker (included as a binary indicators, 0=No, 1= Yes)
- Number of previous child protection plans
- The main need for which child started to receive services for this referral (if applicable), as defined in the [CIN census](#) (included as a categorical variable: 0 = Not stated, 1 = Abuse or neglect, 2 = Child's disability/illness, 3 = Parental Disability/illness, 4 = Family in acute stress, 5 = Family dysfunction, 6 = Socially unacceptable, 7 = Low income, 8 = Absent parenting, 9 = Cases other than Children in Need).

In addition, we would have wanted to take into account families (e.g. through adding family fixed effects), however we are reasonably confident data will not be available, so we have refrained from including them.

---

 In the categories defined in the DfE's CIN census.

 We use Pupil Premium Eligibility for the first three years as every child is eligible for free school meals during this period.

 UN High Commissioner for Refugees (UNHCR). (2013, March). *UNHCR's Engagement with Displaced Youth*. <https://www.refworld.org/docid/5142d52d2.html>, p28.

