## Appendix B: Power calculations Stata code

```
steppedwedge, binomial detectabledifference complete(1) vartotal(0) p1(0.06) m(1700) k(1)  
rho(0.00722) alpha(0.05) beta(0.8) steps(5)
```

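### The primary model and the 1.05 pp MDES have no term for residual authority-by-period drift or family correlation, so the 5% test is too liberal if either exists

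*Protocol*

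**What the plan says.** Under Primary Analysis the protocol specifies a logistic mixed model with a treatment indicator, period dummies common to all authorities, individual covariates X, authority-level time-varying covariates Z_at, and one random term, which "is a (normally distributed) random intercept at the level of the cluster". There is no authority-by-period term. Significance is judged at 5%. On standard errors the section says "Due to the small number of clusters, we cannot cluster or bootstrap standard errors via any conventional method", and a wild bootstrap with a small-cluster correction will only be considered.

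On families, the list of individual covariates says the team would have liked to account for them: "however we are reasonably confident data will not be available, so we have refrained from including them".

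Under Sample size / MDES calculations the protocol states "We are powered to detect an effect size of 0.0105". Appendix B shows the command: "steppedwedge, binomial detectabledifference complete(1) vartotal(0) p1(0.06) m(1700) k(1") followed by "rho(0.00722) alpha(0.05) beta(0.8) steps(5"). The only correlation input is the ICC. A note at the head of the sample size section says the calculation will be checked by simulation and the protocol updated before outcome data are collected. It does not say what correlation structure those simulations will use.

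**The concern.** A constant authority intercept removes differences between authorities that stay fixed, and the period dummies remove movement that all five share. What is left is an authority moving on its own from one half-year to the next. In a stepped wedge with one authority per step, that movement is hard to tell apart from a treatment effect. If the model has no variance term for it, the reported standard error is too small. With about 1,700 children per authority-period the binomial error is so small that even modest drift matters.

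The protocol itself gives reason to expect such movement. The Context section says authorities were chosen for high and/or rising looked-after rates and reports that two had changed Ofsted judgement. The Risks table rates unanticipated authority changes, such as in assessment thresholds, as medium likelihood. Correlation between siblings in the same authority-period acts in the same direction.

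At stake are the error rate and interval of the primary result, whose coefficient also feeds the Cost Benefit Analysis, and the MDES against which a null result will be read.

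**Working it through.** **Inputs from the protocol.** Baseline rate 0.06, 1,700 children per cell, ICC 0.00722, two-sided alpha 0.05 and power 0.80 (sample size table and Appendix B). Five authorities and six periods, the sample being built from "the number of local authorities in the trial and the six periods of the stepped-wedge implementation", with one authority crossing over per step.

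**Reproducing the stated MDES (Hussey-Hughes variance).**
- p(1−p) = 0.06 × 0.94 = 0.0564.
- Between-authority variance τ² = 0.00722 × 0.0564 = 4.07e-4, an SD of 2.02 pp.
- Sampling variance of a cell rate σ² = 0.0564 × (1 − 0.00722)/1700 = 3.29e-5.
- I = 5, T = 6, U = 15, W = 55, V = 55.
- Var = Iσ²(σ² + Tτ²) / [(IU − W)σ² + (U² + ITU − TW − IV)τ²] = Iσ²(σ² + 6τ²) / [20σ² + 70τ²] = 4.08e-7 / 0.02916 = 1.398e-5.
- SE = 0.003739. MDES = 2.8016 × 0.003739 = 0.01048, which matches the stated 0.0105.

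The arithmetic is right, but it corresponds to CAC = 1 and independent children.

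**Adding drift (CAC assumed).** Split τ² into a constant part, CAC × τ², and an independent part for each authority-period, (1 − CAC) × τ². At CAC 0.90 the second part is 4.07e-5, already larger than σ². I kept the planned estimator and its reported SE of 0.003739 and computed its true SE under this covariance. A hand check is √[(σ² + (1 − CAC)τ²)/σ²]: at CAC 0.90 this is √(7.37e-5 / 3.29e-5) = 1.50, against 1.49 in full.
- Type I error of the planned test = 2 × Φ(−1.96 × 0.003739 / true SE).
- Its rejection rate at 1.05 pp ≈ Φ[(0.0105 − 1.96 × 0.003739) / true SE].
- MDES and power in the last two columns are for a correctly sized generalised least squares test using the true covariance.

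| CAC (assumed) | Drift SD, pp | True / reported SE | Planned test: type I | Planned test: rejects at 1.05 pp | Correct test: MDES, pp | Correct test: power at 1.05 pp |
|---|---|---|---|---|---|---|
| 1.00 | 0 | 1.00 | 5% | 80% | 1.05 | 80% |
| 0.99 | 0.20 | 1.06 | 6% | 79% | 1.11 | 76% |
| 0.95 | 0.45 | 1.27 | 12% | 75% | 1.33 | 60% |
| 0.90 | 0.64 | 1.49 | 19% | 72% | 1.56 | 47% |
| 0.80 | 0.90 | 1.86 | 29% | 68% | 1.92 | 33% |

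A simulation of the random-intercept logistic model (600 null trials per scenario, no covariates) gave type I error of 14%, 19% and 32% at CAC 0.95, 0.90 and 0.80. The mean reported SE stayed near 0.066 on the logit scale while the actual SD of the estimate rose to 0.084, 0.103 and 0.126.

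**Adding siblings (assumed).** Two sampled children per family with correlation 0.5 give a design effect of 1 + (2 − 1) × 0.5 = 1.5 on σ². With CAC = 1 the true SE is 1.22 times the reported SE, type I error is about 11% and the correct MDES is 1.28 pp. With CAC 0.90 as well, the figures are about 23% and 1.72 pp.

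**Permutation test.** Two high-readiness and three low-readiness authorities allow 2! × 3! = 12 orders, so the smallest attainable p-value is 1/12 = 0.083.

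**The case against.** The strongest reply is that the model is not blind to drift. Z_at lists eight time-varying authority covariates, including caseload, staff turnover, assessment numbers and other innovation programmes, and these can absorb some of it. That stands. A reader might infer that the model assumes authorities never move apart, but it assumes only that nothing is left after X and Z_at. The CAC values above must therefore be read as residual. Z_at is entered only where available, possibly from yearly proxies, and plays no part in the MDES.

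A second tempting reading is that the planned test has only 60%, 47% or 33% power at CAC 0.95, 0.90 or 0.80. It does not. Those figures belong to a test held at 5%. The planned test would still reject about 75%, 72% or 68% of the time, though only because its size is inflated.

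Third, the size of the problem is not in the documents, and at CAC 0.99 it is small. That also stands. The sibling omission is openly disclosed as a data limit, and the design effect of 1.5 supposes that every child has one sampled sibling.

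Fourth, the protocol has safeguards: a possible wild bootstrap, a permutation test, provisional power figures, and an admission under Randomisation that the small strata weaken robustness. None of these secures the 5% level. The bootstrap is optional, the permutation test is a sensitivity analysis that cannot reach 0.05, and the simulations are not committed to a different correlation structure.

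**Conclusion.** The point holds for residual drift and family correlation. The direction is certain: any residual CAC below 1, or any positive sibling correlation within an authority-period, makes the reported SE too small. The size is conditional on values the protocol does not give. Across an assumed residual CAC of 0.99 to 0.80, type I error runs from about 6% to 29% and the correct MDES from about 1.11 to 1.92 pp. The figures use the unadjusted ICC and baseline rate.

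The main consequence is a false-positive primary finding with an interval that is too narrow. The consequence for a null result is milder, because the planned test keeps much of its rejection rate. The documents do not support saying that the error rate and power have already failed by a known amount. They do support saying that nothing in the plan protects them, and that the flat MDES claim rests on the most favourable case.

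**What to change.** Before outcome data are obtained:

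1. Add an authority-by-period random intercept to the primary model. Alternatively, analyse the 30 authority-period rates, adjusted for individual covariates, with authority and period fixed effects and an estimated residual variance.
2. Test the treatment effect against a t distribution with df = 30 − 5 − 5 − 1 = 19, minus the number of authority-level covariates retained, and state which Z_at are kept. Keeping all eight, one parameter each, leaves 11.
3. Restate the MDES as a range over CAC 0.8 to 1.0 and family design effect 1.0 to 1.5, and use the same structure in the promised simulations.

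The new term needs no family identifiers. It absorbs correlation among siblings who enter in the same authority-period. It does not cover siblings who enter in different periods, which can happen because each child enters at their own first referral.

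**Cost if the current assumptions hold.** With authority fixed effects the SE is 0.003757 (MDES 1.053 pp with normal quantiles). With 19 df the MDES is (2.093 + 0.861) × 0.003757 = 1.11 pp. With 11 df it is (2.201 + 0.876) × 0.003757 = 1.16 pp. Both are before any loss from collinearity between Z_at and treatment. Otherwise the change is to analysis wording, with no extra data.

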## Design

The study design of the impact evaluation is a cross-sectional stepped-wedge cluster randomised controlled trial, where the timing of implementation is staggered across local authorities. The point at which local authorities begin implementing the intervention is selected at random, constrained by their level of readiness to implement the model. In this way, all the local authorities in the sample will eventually implement the Family Safeguarding model, but randomising the start date of the implementation of Family Safeguarding will allow service users in the local authorities that have not yet implemented the programme to act as a control group against service in local authorities where Family Safeguarding has already been implemented.

Given that, prior to the evaluation, there was already an existing need to stagger roll-outs over time, this means that nobody will be denied a service that they might otherwise have received. Local authorities implementing on different timescales will also allow us to take time-based effects into account, with every local authority also acting as a control group for itself over time.

RCT Design Table		
Trial type and number of arms		Stepped wedge cluster randomised controlled trial, two arms
Unit of randomisation		Local authority
Stratification variables		Low/High readiness to implement
Primary outcome	variable	Whether or not the child has become looked after
	measure	Coded 1 if the child has become looked after at any point within 18 months of the referral. Coded 0 if the child has not become looked after within this period.
	sample	Children aged 0-12 that have been referred within the trial period.

Secondary outcome 1	variable	Whether or not the child has returned to statutory services, following a CPP
	measure	Coded 1 if the child finishes a CPP and then returns to statutory services (i.e. begins a new CPP, CIN plan or becomes CLA) within 36 months of the referral start date, coded 0 if they have not re-entered statutory services within this time period.
	sample	Children aged 0-12 that have been referred within the trial period without them going into care.
Secondary outcome 2	variable	CPP plan duration
	measure	Discrete variable equal to the number of days that the child has been on a single CPP. Plan length is recorded up to 24 months from the start of the CPP and censored for larger values.

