## Randomisation

The level of randomisation is at the local authority level. Due to the stepped-wedge evaluation design, we randomise the order in which local authorities implement the programme, in six month intervals, rather than which local authority implements the model. The randomisation will be stratified by the level of readiness of participating local authorities. Each local authority will be classified as either 'high readiness', for those that are in a position to implement the model sooner, and second for the 'low readiness' authorities, for those that will need longer to implement the model. Two local authorities were identified as 'high readiness', and three as 'low readiness'.

The two local authorities classified as 'high readiness' will be randomly assigned to implement the model either first or second. Those classified as 'low readiness' will also have the order randomised in which they will implement the model, following the high readiness local authorities (so they will be the third, fourth, and fifth local authorities to implement the model).

The division of local authorities into more or less ready tranches is meant to avoid implementation failure caused by choosing local authorities to receive the intervention that are not yet ready. The assessment of readiness was conducted by the developing local authority Hertfordshire in collaboration with the Department for Education (DfE). Our strata are thus very small strata (2-3), which normally would be avoided but was necessary in order to be able to implement the evaluation. However it is a notable constraint on our randomisation, that will affect the robustness of our results. This will be reflected in the evidence strength rating awarded to the final study.

To avoid potential contamination, local authorities whose implementation start date has not yet passed have to commit to business-as-usual practices to enable a treatment and control group comparison in each time period. However, they will be given permission to begin preparation to implement, so long as it would not influence the current practice in the local authority.

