### Exploratory Analysis

#### High and low readiness of local authorities

Since the randomisation of the implementation date was stratified by the readiness of local authorities to implement Family Safeguarding, we explore a potential difference in effects of the implementation of Family Safeguarding between high and low readiness authorities.

$$\text{logit}(Y_{iat}) = \beta_0 + \alpha_{0a} + \beta_1 FS_{iat} + \beta_2 HR_a + \beta_3 HR_a * FS_{iat} + \sum_{i=1}^5 \beta_{i+3} I(t=i) + \gamma X_{iat} + \rho Z_{at} + \varepsilon_{iat}$$

Where:

- $HR_a$  is an indicator that is equal to 1 if the authority belongs to the high readiness group that first implements the programme, and 0 if they belong to the 'less ready' group.
- $HR_a * FS_{iat}$  is an interaction term that will allow for differential effects of the model on the local authorities in the high readiness tranche versus the low readiness tranche.  $\beta_3$  will be zero if the intervention affects the likelihood of a child entering care equally in both groups of local authorities.

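### The primary model omits the readiness stratum that fixes rollout order, so a small part of any constant high/low readiness difference enters the treatment effect

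*Protocol*

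**What the plan says.** The RCT Design Table (Design) gives the stratification variable as "Low/High readiness to implement". Under Randomisation, two high-readiness LAs are randomised between first and second place. The three low-readiness LAs are randomised among the remaining places, "so they will be the third, fourth, and fifth local authorities to implement the model".

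The equation under Primary Analysis is written out in full. It contains a "random intercept at the level of the cluster", the treatment indicator FS, five period dummies, individual covariates X and an LA-level term Z, which "is a vector of time-varying local authority characteristics, such as the number of children per local authority or the turnover rate of staff". Readiness is in neither of the two covariate lists under Covariates. It enters a model only in the exploratory section on high and low readiness, where HR "is an indicator that is equal to 1 if the authority belongs to the high readiness group that first implements the programme" and is interacted with FS. Secondary Analysis gives the binary secondary outcomes the primary specification.

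**The concern.** Treated time is tied to stratum by design. In the five-LA, six-period layout, high-readiness LAs are treated for 5/6 and 4/6 of the periods (mean 75%) and low-readiness LAs for 3/6, 2/6 and 1/6 (mean 33%). A random intercept, unlike LA fixed effects, keeps some between-LA information about the treatment effect. It is valid to use that information only if the LA level is unrelated to treatment timing, and randomisation secures this within strata only. If the strata differ in their underlying care-entry rate, part of that difference is counted as a treatment effect.

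A difference is plausible. The Context section shows that both early LAs were rated as requiring improvement at first rollout, while the later three include one good and one outstanding. These ratings do not give the size or direction of any gap in care entry.

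**Working it through.** **Inputs.** Baseline rate 0.06, 1,700 children per LA per period, ICC 0.00722, two-sided alpha 0.05, power 0.8, five steps with one LA each (Sample size / MDES calculations; Appendix B). The high-minus-low gap in care entry is not given, so gaps of 1 to 6 pp are assumed. As in the protocol's power calculation, the scale is linear with equal cells and no covariates.

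**Reproducing the MDES.** Total variance = 0.06 × 0.94 = 0.0564.
- Between-LA variance τ² = 0.00722 × 0.0564 = 0.000407 (SD about 2.0 pp).
- Cell variance σ² = 0.99278 × 0.0564 / 1,700 = 0.00003294.
- Weight on between-LA information: k = σ² / (σ² + 6τ²) = 0.0133.
- For this layout the Hussey-Hughes variance reduces to 3σ² / (7 + 5k) = 0.00001398, so SE = 0.003739.
- MDES = 2.8016 × 0.003739 = 0.01048.

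This agrees with the protocol: "We are powered to detect an effect size of 0.0105".

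**Leak with the variance known.** Use the readiness indicator as the outcome in the same weighted model. The treatment coefficient is 9k / (7 + 5k).
- ICC 0.00722: 0.1197 / 7.0665 = 1.7%.
- ICC 0.003: 4.0%. ICC 0.001: 10.8%. Zero LA variance (k = 1): 9/12 = 75%.
- With a readiness main effect or LA fixed effects: 0.

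At the planning ICC, gaps of 1, 2, 3, 4 and 6 pp give biases of 0.017, 0.034, 0.051, 0.068 and 0.102 pp. The largest is 9.7% of the MDES and 0.27 SE.

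**Which gaps go with which ICC.** The model omits readiness, so the gap itself sits inside the LA variance. A 3 pp gap split 2 versus 3, with no other LA variation, gives 0.24 × 9 = 2.16 pp² (2.7 with an n-1 divisor). That is an ICC of 0.0038 to 0.0048, a leak of 2.5 to 3.2% and a bias of 0.08 to 0.09 pp.

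**Leak with the variance estimated.** Simulated LA-period means, Wald test at 1.96, no true effect, maximum likelihood (ML) unless stated:

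| Gap | LA SD within stratum | Mean bias | Rejection without / with readiness term |
|---|---|---|---|
| 2 pp | 2 pp | 0.03 pp | 3.7% / 4.2% |
| 2 pp | 1 pp | 0.07 pp | 6.0% / 5.3% |
| 4 pp | 1 or 2 pp | 0.05 to 0.06 pp | 5.2-5.3% / 5.2-6.5% |
| 3 pp | 0 | 0.10 pp (restricted ML 0.08) | not tabulated |
| 2 pp | 0 | 0.15 pp | 7.7% / 4.2% |
| 1 pp | 0 | about 0.2 pp (restricted ML) | about 14% / about 4% |

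These rest on a few hundred runs each (600 in the ML rows, 300 for the 3 pp row). A repeat of the last row with 4,000 runs and σ² held at the value above gave 0.21 pp and 14% under restricted ML, and 0.27 pp and 18% under ML. Rejection with the readiness term was 5 to 6%.

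**Cost at the planning ICC.**
- LA fixed effects: variance 3σ²/7, SE 0.003757, MDES 1.053 pp.
- Readiness term: variance 12σ² / (28 + 5k), SE 0.003753, MDES 1.051 pp.

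**The case against.** The strongest reply is that the effect is negligible at the planning values, because the random intercept already removes about 98% of a constant stratum difference. That stands, and it is why this is a refinement.

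A reader might instead infer a large bias by multiplying a 3 pp gap by the 10.8% leak at ICC 0.001, which gives 0.32 pp. The documents do not support this. At that ICC the whole between-LA SD is √(0.001 × 0.0564), about 0.75 pp, so an unmodelled 3 pp gap could not coexist with it. A larger gap raises the estimated LA variance and shrinks the share that leaks.

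It can also be said that the protocol already deals with the matter. Randomisation concedes that the very small strata weaken robustness and says the evidence rating will reflect this. The exploratory model contains a readiness main effect. Neither corrects the primary estimate: the first is a caveat, and in the second the FS coefficient is the effect in low-readiness LAs only, because of the interaction. The time-varying LA covariates might absorb some of a level difference, but nothing ensures it.

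Finally, the MDES comparison treats the variance as known. A readiness term across five LAs leaves 3 rather than 4 degrees of freedom for the LA variance, so a near-zero estimate becomes more likely. That stands and favours LA fixed effects.

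**Conclusion.** The point holds as a minor, cheaply corrected mismatch between the stratified randomisation and the primary model. It is not a major bias in the headline result. Expected bias is about 0.05 pp at the planning ICC for an assumed 3 pp gap, and about 0.1 pp or less for gaps of 2-3 pp once the LA variance is estimated. The exceptions need LAs in the same stratum to be practically identical: 0.15 pp at a 2 pp gap, and about 0.2 pp, with clear inflation of false rejection, at a 1 pp gap.

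The omission and the zero leak after correction follow from the protocol's text and design. The sizes rest on assumed gaps, the linear scale, equal cells and no covariates. Nothing was calculated for the binary secondary outcomes; they are included only because they share the specification.

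**What to change.** In the primary model, and in the binary secondary models that use its specification, preferably replace the random LA intercept with LA fixed effects. These contain the stratum and do not depend on an LA variance estimated from five LAs. At the least, add the HR main effect already defined in the exploratory section.

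The cost at the planning ICC is 0.005 pp of MDES for fixed effects (1.048 to 1.053) or 0.003 pp for the readiness term (1.048 to 1.051). The second figure does not count the lost degree of freedom. No extra data are needed. The protocol already plans power simulations and an update before outcome data are collected, so the change can be made then. State in the text that neither option protects against time trends that differ between the readiness groups.
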